8.1.7.1. Body Surface Area – Efficacy (BSA Efficacy)

BSA Efficacy will be derived from the sum of the BSA in handprints across 4 body regions assessed as part of the EASI assessment ([Table 4](#)). Handprint refers to that of each individual participant for their own measurement. The BSA Efficacy ranges from 0 to 100%, with higher values representing greater severity of AD. Assessments will be collected at various time points as described in the [Schedule of Activities](#).

CCI

8.1.9. Patient-reported Outcomes (PROs)

Participants will complete the PROs at the clinic prior to other clinical activities and study intervention administration. The PROs should be checked for completeness by the study site staff before proceeding with other steps of the clinical visit procedures. Compliance with scheduled PROs activities will be monitored. Delegated site staff will oversee the administration of PROs at site visits to ensure protocol compliance. Participants are given a diary to complete the Peak Pruritus NRS and Night Time Itch Scale on a daily basis. Delegated site staff will review compliance at each visit and counsel as appropriate. If a participant has repeated non-compliance, the participant should be re-trained.

CCI

8.1.9.1. Peak Pruritus Numerical Rating Scale (NRS)

The severity of itch (pruritus) due to AD will be assessed using the Peak Pruritus NRS, a validated horizontal NRS.^{21,22} Participants will be asked to assess their worst itching due to AD over the past 24 hours on an NRS anchored by the terms “no itch” (0) and “worst itch imaginable” (10). This item will be administered to all participants. Participants will enter Peak Pruritus NRS assessment into a diary. The Peak Pruritus NRS as it is assessed on the day of the baseline visit will be included in the evaluation of Inclusion Criterion 2.

The Peak Pruritus NRS should be completed as per [Schedule of Activities](#).

8.1.9.2. Night Time Itch Scale

Severity of Night Time Itch

The severity and frequency of itch (pruritus) during the night due to AD will be assessed using the Night Time Itch Scale. Participants will be asked to assess their worst itching due to AD during their most recent night's sleep on an NRS anchored by the terms "no itch" (0) and "worst itch imaginable" (10). The frequency of itch will be assessed using a 5-point qualitative scale, with responses including "Never", "Rarely", "Sometimes", "Often" and "Almost Always". This item will be administered to all participants.

The Night Time Itch Scale should be completed as per [Schedule of Activities](#).

8.2. Safety Assessments

Planned time points for all safety assessments are provided in the [Schedule of Activities](#).

8.2.1. Physical Examinations and Medical History

- Complete AD disease history includes collection of details of AD at Screening: AD diagnosis, the use of topical treatments, systemic treatments and other treatments for AD. Medical history in addition to AD history including disease duration will be collected at screening. Medical history also includes history of alcohol and tobacco use. Smoking status and average weekly alcohol consumption (units/week) will be collected, where a unit contains 12 g of pure alcohol, an amount equivalent to that contained in 5 oz/150 mL (a glass) of wine, 12 oz/360 mL of beer, or 1.5 oz/45 mL of 90 proof of spirits.
- Complete medication history of all prescription or nonprescription drugs, and dietary and herbal supplements taken within 28 days prior to the planned first dose, except as noted below:

The following timeframe prior to the planned first dose must be used for collection of the following Current/Prior Medications:

- 1 year: Previous non-systemic drug treatments for AD including topical treatments;
- Lifetime history of previous systemic treatment for AD and reason for stopping any systemic treatment for AD;
- Lifetime history of intolerance/allergy to any drug, regardless of indication.
- A complete physical examination will include, at a minimum, assessments of the general appearance; skin; head, eyes, ears, nose and throat (HEENT); mouth, heart;

lungs; breast (optional); abdomen; external genitalia (optional); extremities; neurologic function; and lymph nodes. Complete physical examinations must be performed by the investigator, sub-investigator or a qualified health professional per local guidelines. Height (inches or centimeters) and weight (lbs. or kg) will be measured and recorded in the source document at the screening visit. Height and weight will be measured without the participant wearing shoes. Weight (lbs. or kg) will continue to be measured and recorded at various time points described in the [Schedule of Activities](#).

- A targeted physical examination will include, at a minimum, assessments of the skin, heart, lungs, and abdomen and examination of body systems where there are symptom complaints by the participant. Targeted physical examinations must be performed by the investigator, sub-investigator or a qualified health professional per local guidelines.
- Investigators should pay special attention to clinical signs related to previous serious illnesses.

8.2.2. Vital Signs

- Vital signs (sitting blood pressure, pulse rate, respiratory rates, and temperature) will be measured after 5 minutes of rest as indicated in the [Schedule of Activities](#).
- Pulse rate and blood pressure will be assessed pre-dose. The same method should be used consistently throughout the study.
- Pulse rate and blood pressure measurements will be assessed in a seated position, back supported, and arms bared (free of restrictions such as rolled-up sleeves, etc.) and supported at heart level. Measurements should be taken on the same arm at each visit (preferably non-dominant) with a completely automated device. Manual techniques will be used only if an automated device is not available.
- Pulse rate and blood pressure measurements should be preceded by at least 5 minutes of rest for the participant in a quiet setting without distractions (eg, television, cell phones). Participants should refrain from smoking or ingesting caffeine during the 30 minutes preceding the measurements.

8.2.3. Chest X-Ray

Chest X-ray (posterior-anterior and lateral views) or other appropriate diagnostic image (ie, chest computed tomography or MRI) at screening or within 12 weeks prior to Study Day 1. Such imaging must be read by a qualified radiologist and show no evidence of current, active TB. Documentation of the official reading must be located and available in the source documentation.

8.2.4. Tuberculosis Testing

At the time of screening, all participants will undergo tuberculosis (TB) testing unless performed within 12 weeks of Day 1. QFT-G is the preferred testing method. If the QFT-G test cannot be performed, or if the results cannot be determined by the reference laboratory to be either positive or negative, then participants may be screened using the PPD test with approval of the Pfizer clinician.

In addition to TB testing as specified in this clinical protocol, a chest X-ray (or other appropriate diagnostic image (see [Section 8.2.3](#)) is recommended.

QFT-G test is an in vitro diagnostic test using a peptide cocktail simulating early secretory antigen 6 (ESAT-6), cell filtrate protein 10 (CFP-10), and TB 7.7 proteins to stimulate cells in heparinized whole blood. Detection of interferon- γ by Enzyme-Linked Immunosorbent Assay (ELISA) is used to identify in vitro responses to these peptide antigens that are associated with *Mycobacterium tuberculosis* infection. QFT-G is an indirect test for *M. tuberculosis* infection (including disease) and is intended for use in conjunction with risk assessment, radiography and other medical and diagnostic evaluations.

A blood sample (approximately 3 mL) will be collected at screening for QFT-G testing. Following sample processing, the sample will be shipped to the sponsor's designated reference laboratory for testing. The procedure for processing and preparing the sample for shipment is described fully in the laboratory manual, which will be provided to investigators.

Should the PPD test be required, the test must be administered and evaluated by a health care professional 48 to 72 hours later, unless performed and documented within the last 3 months. The test should be performed according to local standards with induration of <5 mm required for inclusion.

8.2.5. Special Safety Assessment

In the event of a suspected opportunistic infection, effort should be made to identify the pathogen utilizing laboratory or other methods appropriate to the clinical situation.

In case of a suspected viral skin infection (eg, herpes zoster, herpes simplex or eczema herpeticum), a specimen for viral DNA may be analyzed locally for confirmation and results provided to the adjudication committee to support evaluation.

For participants with a past history of oral or genital herpes simplex virus infection and a presentation consistent to prior infections, further laboratory analysis may be performed at the discretion of the investigator.

8.2.6. Skin Type Assessment

As part of baseline characteristics, a skin type assessment will be done using the Fitzpatrick Skin Type assessment (see [Appendix 12](#)). This is used to classify a person's skin type by their response to sun exposure (ie, burning or tanning).

8.2.7. Electrocardiograms

- Single 12-lead ECG will be obtained using an ECG machine that automatically calculates the heart rate and measures PR, QRS, QT, and [QTc] intervals. Refer to [Appendix 10](#) for [QTc] withdrawal criteria. ECGs will be done locally.
- The ECG should be performed after the participant has rested quietly for at least 10 minutes in a supine position.
- A participant's screening ECG must not demonstrate clinically significant abnormalities prior to randomization.

8.2.8. Clinical Safety Laboratory Assessments

- See [Appendix 2](#) for the list of clinical laboratory tests to be performed and the *Schedule of activities* for the timing and frequency.
- Participants must abstain from all food and drink (except water and non-study medications) for an 8-hour overnight fast prior to labs that include the lipid profile panel on Day 1 and Week 12. All other labs do not require fasting.
- Sample collection, labeling, storage, and shipping information can be found in the laboratory manual.
- The investigator must review the laboratory report, document this review, and record any clinically relevant changes occurring during the study in the AE section of the CRF. The laboratory reports must be filed with the source documents. Clinically significant abnormal laboratory findings are those which are not associated with the underlying disease, unless judged by the investigator to be more severe than expected for the participant's condition.
- All laboratory tests with values considered clinically significantly abnormal during participation in the study or within 28 days after the last dose of study intervention should be repeated until the values return to normal or baseline or are no longer considered clinically significant by the investigator or medical monitor.
 - If such values do not return to normal/baseline within a period of time judged reasonable by the investigator, the etiology should be identified and the sponsor notified.
 - All protocol-required laboratory assessments, as defined in [Appendix 2](#), must be conducted in accordance with the laboratory manual and the [Schedule of Activities](#).
 - If laboratory values from non-protocol specified laboratory assessments performed at the institution's local laboratory require a change in participant management or are considered clinically significant by the investigator (eg, SAE or AE or dose modification), then the results must be recorded in the CRF.

8.2.8.1. Hepatitis Testing

Hepatitis B testing: HB surface antigen (HBsAg), HB core antibody (HBcAb), HB surface antibody (HBsAb), HBV DNA.

Interpretation of Hepatitis B Testing Results:

HBsAg negative and HBcAb negative: Participant is eligible for the study;

HBsAg positive and HBcAb negative: Participant is excluded from study participation;

HBsAg negative and HBcAb positive and HBsAb negative: Participant is excluded from study participation.

HBsAg negative and HBcAb positive and HBsAb positive: Participant may be eligible for the study:

- Participants who are HBsAg negative, HBcAb positive, and HBsAb positive at Screening will have reflex testing for HBV DNA. Participants who have HBV DNA above lower limit of quantification (LLQ) will be excluded. Participants who are HBV DNA negative or below LLQ may be randomized but will have repeat HBV DNA testing at Week 12 (or Early Termination).

Hepatitis C testing: Hepatitis C Antibody (HCV Ab), Hepatitis C Viral RNA (HCV RNA for confirmation of positive HCV Ab result).

Interpretation of Hepatitis C Testing Results:

Participants who are positive for hepatitis C viral antibody (HCVAb) and HCV RNA will be screen failed.

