Blood Cell and platelets derive from a common progenitor. Blood for platelet and red blood cell (RBC) counts will be collected and analyzed at all scheduled time points to characterize the potential mechanism by which platelet counts decrease in a dose-dependent and self-limited manner after abrocitinib administration. OLINK proteomics will be used to analyze biomarkers in serum, including 4 panels of inflammatory and cardiovascular measures.

At the end of the 12-week study treatment, qualified participants will have the option to enter the long-term extension (LTE) Study B7451015. Participants discontinuing early from this study will undergo a 4-week off-treatment follow-up period.

Disclosure Statement:

This is a Parallel Treatment study with 3 Arms that is Investigator, sponsor, and participant blinded.

Number of Participants:

A total of approximately 51 participants will be randomized in the study.

Intervention Groups and Duration:

Eligible participants will be randomized into 3 intervention groups in the study:

Group 1 (N=17): abrocitinib 200 mg QD for 12 weeks.

[figure not shown]
Group 2 (N=17): abrocitinib 100 mg QD for 12 weeks.

Group 3 (N=17): placebo QD for 12 weeks.

The total duration of participation in the study is up to 20 weeks, including up to 4 weeks for screening, 12 weeks study intervention, and a follow-up period of 4 weeks after study intervention (for those participants who do not enter the LTE study).

Data Monitoring Committee: Yes

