Visit Identifier	Day -28	Day 1 Week 0 Base line	Day 2 Week 0	Day 4 Week 0	Day 8 Week 1 (by Phone)	Day 15 Week 2	Day 29 Week 4	Day 43 Week 6	Day 57 Week 8	Day 85 Week 12 (EOT/ET)	Day 113 Week 16 (EOS)	Visit 11 is 4 weeks after last dose in case of early study termination.	
	Visit 1	Visit 2	Visit 3	Visit 4	Visit 5	Visit 6	Visit 7	Visit 8	Visit 9	Visit 10	Visit 11		
Hepatitis B (HBsAg, HBsAb and HBcAb) and Hepatitis C (HCV Ab, HCV RNA)	X											See Section 8.2.8.1	
HBV DNA (Only when HBsAg-, HBcAb+, HBsAb+ at screening)	X										X	See Section 8.2.8.1	
Tuberculosis test	X											See Section 5.2 and Section 8.2.4	
Study Treatment													
Randomization		X											
Drug dispensing		X					X		X				
Drug accountability						X	X		X	X			

	Screening	Intervention Period											Follow-up	Notes
Visit Identifier	Day -28	Day 1 Week 0 Base line	Day 2 Week 0	Day 4 Week 0	Day 8 Week 1 (by Phone)	Day 15 Week 2	Day 29 Week 4	Day 43 Week 6	Day 57 Week 8	Day 85 Week 12 (EOT/ET)	Day 113 Week 16 (EOS)	Visit 11 is 4 weeks after last dose in case of early study termination.		
	Visit 1	Visit 2	Visit 3	Visit 4	Visit 5	Visit 6	Visit 7	Visit 8	Visit 9	Visit 10	Visit 11			
Study intervention treatment		X-----X											At Weeks 4 and 12, study intervention treatment should be taken at the study site to accommodate PK analysis. See Section 8.5	
Assess eligibility for LTE Study B7451015										X				
Clinical Assessments														
Fitzpatrick Skin Type Assessment		X											See Section 8.2.6	
Investigator's Global Assessment (IGA)	X	X				X	X		X	X	X		See Section 8.1.6	
Eczema Area and Severity Index (EASI)	X	X				X	X		X	X	X		See Section 8.1.7	
Skin Biopsies														

	Screening	Intervention Period										Follow-up	Notes
Visit Identifier	Day -28	Day 1 Week 0 Base line	Day 2 Week 0	Day 4 Week 0	Day 8 Week 1 (by Phone)	Day 15 Week 2	Day 29 Week 4	Day 43 Week 6 (by Phone)	Day 57 Week 8	Day 85 Week 12 (EOT/ET)	Day 113 Week 16 (EOS)	Visit 11 is 4 weeks after last dose in case of early study termination.	
	Visit 1	Visit 2	Visit 3	Visit 4	Visit 5	Visit 6	Visit 7	Visit 8	Visit 9	Visit 10	Visit 11		
Target lesion(s) identification		X										See Section 8.1.2	
Lesional skin punch biopsy sampling		X				X (Optional)	X			X		See Section 8.1.2	
Non-lesional skin punch biopsy sampling		X								X (Optional)		See Section 8.1.2	
Examination of Post-biopsy Site(s)		X	X	X		X	X		X	X	X	See Section 8.1.2	

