4. STUDY DESIGN

4.1. Overall Design

[figure not shown]
This is a randomized, double-blind, placebo-controlled, parallel-group, Phase 2a study to investigate the mechanism of action of abrocitinib by correlating efficacy outcomes with changes from baseline in key skin and blood biomarkers in adult participants ≥ 18 years of age with moderate-to-severe AD. Participants will be screened within 28 days prior to the first dose of study intervention to confirm study eligibility. A total of approximately 51 participants will be randomized in a 1:1:1 ratio to receive abrocitinib 200 mg QD, abrocitinib 100 mg QD, or matching placebo QD for 12 weeks. Refer to Section 1.2 for a study schema.

The total duration of participation in the study is up to 20 weeks, including up to 4 weeks for screening, 12 weeks study intervention, and a follow-up period of 4 weeks after study intervention. Qualified participants completing 12 weeks of treatment with study intervention will have the option to enter the long-term extension (LTE) study B7451015. Participants discontinuing early from this study will undergo a 4-week off-treatment follow-up.

Participants who have chronic moderate-to-severe AD as defined per the inclusion criteria will be enrolled in this study. Eligible participants must have a documented history, within 6 months of the screening visit, of inadequate response to treatment with medicated topical therapy, or must have required systemic therapies for control of their disease. Investigators, participants, and the sponsor study team will be blinded as to treatment group assignment. Prior to any study procedure the informed consent will be obtained at the screening visit.

Participants will be screened within 28 days prior to the first dose of study intervention to confirm study eligibility. During the screening period, treatments for AD will be washed out, as applicable, according to eligibility requirements. All treatments for AD must have been washed out prior to Day 1 (see Section 5.2). Participants who continue to meet eligibility criteria at baseline will undergo Baseline/ Day 1 assessments and will be randomized in a 1:1:1 ratio to receive abrocitinib 200 mg (N=17) or abrocitinib 100 mg QD (N=17) or matching placebo QD (N=17) from Day 1.

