4.4. End of Study Definition

A participant is considered to have completed the study if he/she has completed all phases of the study including follow-up assessments after the End of Treatment (EOT) or rolled over into LTE Study B7451015 after EOT. Details of early termination are provided in Section 7.

The end of the study is defined as the date of the last study visit shown in the [Schedule of Activities](#) for the last participant at the study sites.

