Table 7. Protocol-Required Safety Laboratory Assessments

Laboratory Assessments	Parameters
	CD8+ T cells (CD3+CD8+) NK cells (CD3-CD16+CD56+) B cells (CD3-CD19+)

1. Lipid profile panel requires at least an 8 hour fast. Lipid profile panel will be completed at Day 1 and Week 12, and will include total cholesterol, LDL, HDL, and triglycerides.
2. Microscopy performed at all visits and culture as appropriate.
3. At Screening only. HIV testing will be performed for all participants.
4. HBsAb reflex testing only if HBsAg negative but HBcAb positive. HCV RNA is reflex testing only if HCVAb is positive.
5. Participants who are HBsAg negative, HBcAb positive, and HBsAb positive will have reflex testing for HBV DNA.
6. Pregnancy testing for all WOCBP.
7. PPD results should be read within 48 to 72 hours.
- C** 9. All study-required laboratory assessments will be performed by a central laboratory, with the exception of: urine pregnancy tests, which will be performed on the Day of the study visits per the [Schedule of Activities](#).

Investigators must document their review of each laboratory safety report.

Laboratory results that could unblind the study will not be reported to investigative sites or other blinded personnel until the study has been unblinded.

10.3. Appendix 3: Adverse Events: Definitions and Procedures for Recording, Evaluating, Follow-up, and Reporting

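### Protocol Section 8.2.8.1 sets the repeat HBV DNA test at Week 12 or early termination, but the Schedule of Activities, as extracted, marks it at Week 16 (EOS) and leaves Week 12 empty

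*Protocol*

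**What the plan says.** Three places in the protocol bear on when the repeat test is done.

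- **Section 8.2.8.1** (Hepatitis Testing) lets participants with this serology be randomized if HBV DNA is negative or below the quantification limit, and adds that they "will have repeat HBV DNA testing at Week 12 (or Early Termination".
- **Section 1.3** (Schedule of Activities) has a row labelled "HBV DNA (Only when HBsAg-, HBcAb+, HBsAb+ at screening". As extracted, it carries one mark at Screening and one under Day 113, Week 16 (EOS). The Day 85, Week 12 (EOT/ET) cell is blank. The row's note points to Section 8.2.8.1.
- **Appendix 2**, Table 7, footnote 5: "Participants who are HBsAg negative, HBcAb positive, and HBsAb positive will have reflex testing for HBV DNA". It covers the screening reflex test and names no visit for a repeat.

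Two further provisions decide which instruction a site would act on and who would be reached. Section 8.2.8 refers sites to the schedule "for the timing and frequency" of laboratory tests and requires those tests to be done in line with the schedule and the laboratory manual. The Synopsis provides "a follow-up period of 4 weeks after study intervention (for those participants who do not enter the LTE study".

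**The concern.** The text and the schedule appear to give different visits for the same safety test, and nothing in either document says which prevails. The difference is more than a label. Under Section 4.1, "Qualified participants completing 12 weeks of treatment with study intervention will have the option to enter" the extension study, and Section 4.4 counts a participant as having completed if they "rolled over into LTE Study B7451015 after EOT". Such a participant has a Week 12 visit but no Week 16 visit in this study. The test exists because this serology indicates past hepatitis B exposure, and Section 2.3 lists viral reactivation among the potential risks of treatment. A mark under Week 16 would miss extension entrants and would test everyone else some weeks after dosing has stopped.

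**Working it through.** The plan states no figure to reproduce. The check is one of position, followed by simple arithmetic on the consequence.

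**1. Where the mark sits.** Cells are counted along the extracted row: 1 = Screening, 2 = Day 1, 3 = Day 2, 6 = Week 2, 7 = Week 4, 8 = Week 6, 9 = Week 8, 10 = Week 12 (EOT/ET), 11 = Week 16 (EOS), 12 = Notes. The HBV DNA row has marks in 1 and 11, and its note is in 12.

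**2. Is cell 10 reliable in this table?** Eight other protocol rows have a Week 12 timing that is also stated outside the schedule.

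| Protocol row | Marks in cells | Week 12 timing also stated in |
|---|---|---|
| Lipid panel | 3, 10 | Protocol 8.2.8 |
| Serum proteomics | 2, 6, 7, 10 | Protocol 8.8 |
| Lesional biopsy | 2, 6, 7, 10 | Protocol 8.1.2 |
| Non-lesional biopsy | 2, 10 | Protocol 8.1.2 |
| Weight | 1, 10 | SAP 6.8.3 |
| Vital signs | 1, 2, 6, 7, 9, 10, 11 | SAP 6.8.3 |
| Drug accountability | 6, 7, 9, 10 | SAP 6.7.3 |
| Extension eligibility | 10 | Protocol 4.1 |

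The Week 12 mark falls in cell 10 in 8 of 8 rows. On the HBV row's own table page, dispensing extracts at Day 1, Week 4 and Week 8, which agrees with SAP 6.7.3.

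**3. Evidence against relying on it.** Section 8.2.8 requires fasting for the "lipid profile panel on Day 1 and Week 12", yet the first lipid mark extracts in cell 3 (Day 2) although that row's note is in place. One mark can therefore be a column out in a row that otherwise looks sound.

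**4. Consequence per affected participant if the schedule mark is followed.**

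- Extension entrants: 0 post-screening HBV DNA tests in this study instead of 1.
- Other completers: Day 113 − Day 85 = 28 days later. With ±3 days at each visit, the range is 110 − 88 = 22 to 116 − 82 = 34 days.
- Early terminators: tested at the visit 4 weeks after last dose instead of at the early termination visit.

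**5. How many participants.** The documents do not give the share with this serology. The shares below are assumptions. With 51 participants, the expected number is 51p and the chance of none is (1 − p)^51.

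| Assumed p | Expected number | Chance of none |
|---|---|---|
| 1% | 0.51 | 0.99^51 = 0.60 |
| 2% | 1.02 | 0.98^51 = 0.36 |
| 5% | 2.55 | 0.95^51 = 0.07 |

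**The case against.** The strongest reply is that the whole point rests on one cell of a machine-read table. Besides the lipid mark, the SAP's copy of the schedule (Appendix 7) shows how such errors arise. Its weight and lipid Week 12 marks extract under Week 16, its Week 4 dispensing mark extracts under Week 6, and two photography marks differ by one column from the protocol row although the note is in place. This stands, and it has two effects. The conflict can be claimed only as extracted. And although the SAP's HBV DNA row shows the same pattern, that is not useful corroboration: the SAP table reproduces the protocol's and has displaced rows of its own.

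The second reply is that the row's note already leads to Section 8.2.8.1, where the visit is explicit. That reduces the risk but does not remove it. A site that looked would hold two instructions, and Section 8.2.8 tells it that laboratory tests follow the schedule.

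The third reply is that other safeguards exist. Participants with HBV DNA above the quantification limit are excluded at screening, AST/ALT monitoring continues (Appendix 10), and a baseline sample is kept for viral studies (Section 8.2.8.2). These limit the harm but do not replace the test. The retained sample is from baseline and is analyzed only on suspicion, and the AST/ALT retest trigger is above 3 times the upper limit of normal.

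A reader might also infer that extension entrants go untested for HBV DNA altogether after screening. The documents do not support that. Neither the extension study's testing nor the laboratory manual can be seen, so the statement covers this study only.

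**Conclusion.** The point holds as an apparent inconsistency between Section 8.2.8.1 and the protocol schedule, subject to confirming the cell in the original table. The alignment of the eight check rows and of the HBV row's own note makes the Week 16 position probable, while the displaced lipid mark keeps it short of proven. A reader might conclude that the protocol certainly contains an error; the extracted text alone cannot carry that.

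If the position is confirmed, the effect is the loss of one safety sample per affected extension entrant and a delay of about four weeks for other affected completers. It is confined to a small, possibly empty, serological subgroup whose size is assumed here. No efficacy analysis depends on it. It is more than clerical because the repeat test is a safeguard the protocol itself asks for, but it is a minor point.

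**What to change.** Check the second HBV DNA mark in the original protocol Schedule of Activities. If it is under Week 16 (EOS), move it to Week 12 (EOT/ET). That column serves both Week 12 and early termination, so it matches Section 8.2.8.1 exactly and reaches extension entrants. If the mark is already under Week 12, nothing needs to change. SAP Appendix 7 is an overview copy that feeds no HBV DNA analysis, so it needs no separate action.

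The cost is one table check and at most one mark moved. No test, visit or blood draw is added, since serum chemistry is already scheduled at Week 12.
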